4.4.6. Radiotherapy plan quality requirements

The plan quality is assessed using the established metrics by Shaw et al. (Shaw et al. 1993) as well as by the new ICRU 91 guidelines (ICRU 2017).

The specified values have to be achieved.

Conformity Index:

The Conformity Index is defined as $CI = V_{RI}/TV$, where V_{RI} is the volume of the encompassing prescription isodose and TV is the volume of the planning target volume

Per Protocol: Conformity Index ≥ 1.0 and ≤ 2.0

Acceptable variation: Conformity Index ≥ 0.9 and < 1.0 OR > 2.0 and ≤ 2.5

Major deviation (Unacceptable): all other

Note: In the control arm (SRS), if normal brain tissue constraints can't be met otherwise, the lower boundary for per protocol is decreased to 0.9 and the lower boundary for acceptable variation is lowered to 0.8 (see below).

Coverage:

The Coverage is defined as $Q = I_{min}/I_{pre}$, where I_{min} is the minimum dose, the target receives and I_{pre} is the prescribed dose.

Per Protocol: Coverage ≥ 0.9

Acceptable variation: Coverage 0.8 – 0.9

Major deviation (Unacceptable): all other

Note: In the control arm (SRS), if normal brain tissue constraints can't be met otherwise, the lower boundary for per protocol is decreased to 0.8 and the lower boundary for acceptable variation is lowered to 0.7 (see below).

Homogeneity Index:

The Homogeneity Index is defined as $HI = I_{max}/I_{pre}$, where I_{max} is the maximum dose, the target receives and I_{pre} is the prescribed dose.

Per Protocol: Homogeneity Index ≤ 2

Acceptable variation: Homogeneity Index > 2.0 and ≤ 2.5

Major deviation (Unacceptable): all other

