4.6. Modification of the radiotherapy regimen

In principle, the study protocol does not provide for the interruption or even discontinuation of the specified radiotherapy regimen. This is only possible at the discretion of the responsible radio-oncologist if there is good reason for doing so. Likewise, the individual reference dose, total reference dose and PTV can be modified in such an event at the discretion of the radio-oncologist. The radio-oncologist must make such a decision on an individual patient basis and inform the study center of the decision. (see also the

sections: 4.4.3. Target volume delineation, 4.4.9. Normal Tissue Constraints as well as 4.4.10. Sparing of healthy brain tissue)

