9.3. Patient evaluation categories

If a major eligibility violation occurs, the affected subject will be excluded from the statistical analysis and classified as "ineligible" (in accordance with the ICH E9 statistical principles for clinical trials). Only case reports will be presented for these patients.

All other patients will be included in an intention-to-treat analysis of the primary endpoint. A per-protocol analysis including only those patients who fully completed radiotherapy according to protocol will also be performed, as a sensitivity analysis.

All patients who received at least one dose of radiation treatment according to protocol will be included in the toxicity analysis.

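### Section 9.3 defines the toxicity set by compliance and eligibility as well as exposure, so some irradiated patients can be left out of the toxicity analysis

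*Protocol*

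**What the plan says.** Section 9.3 of the protocol sets out three rules that bear on who is counted for safety.

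- Toxicity set: "All patients who received at least one dose of radiation treatment according to protocol will be included in the toxicity analysis".
- Per-protocol set, in the paragraph before: "A per-protocol analysis including only those patients who fully completed radiotherapy according to protocol will also be performed, as a sensitivity analysis".
- Major eligibility violations: "the affected subject will be excluded from the statistical analysis", followed by "Only case reports will be presented for these patients". No exception is made for safety.

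Other sections give the compliance condition its possible content. Section 4.4.6 grades conformity, coverage and homogeneity as per protocol, acceptable variation, or "Major deviation (Unacceptable): all other". Section 4.6 says "In principle, the study protocol does not provide for the interruption or even discontinuation of the specified radiotherapy regimen", but then allows that "the individual reference dose, total reference dose and PTV can be modified in such an event at the discretion of the radio-oncologist". Section 4.4.10 expressly permits lower SRS prescription doses and relaxed lower limits for conformity and coverage in the SRS arm. Section 4.4.8 has plan quality checked by random sampling during the trial and systematically only once accrual is complete.

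Tolerability (CNS toxicity, in particular radiation necrosis) is the first secondary objective in section 1.6.2. Section 9.4 plans to compare toxicity rates.

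**The concern.** A toxicity population should be defined by exposure. Here it is also conditioned on whether radiation was given as the protocol specifies and, through the eligibility rule, on whether the patient should have been enrolled. Both conditions can remove people who were irradiated and could have been harmed.

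What is at stake is the main secondary comparison. The filter need not remove the same kind or number of patients in each arm. The information needed to apply it fully also arrives late. Section 2.1 describes an open trial, so deciding membership after accrual means deciding it when treatment and toxicity may both be known.

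This is not a detail left to the analysis plan. The protocol itself fixes the population, and an analysis plan that follows section 9.3 would inherit the problem.

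**Working it through.** The document gives no size for the toxicity set and no expected number of plan deviations, so there is no figure to reproduce. The check is a reading of the sections side by side, followed by an illustration on assumed inputs.

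**Step 1. Who is in and who is out under the literal text**

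| Irradiated patient | Relevant section | Status in the toxicity set |
|---|---|---|
| SRS, dose reduced or limits relaxed as allowed | 4.4.10 | In: the protocol permits it |
| FSRT, course changed or stopped after one conforming fraction | 9.3, 4.6 | In: one dose is enough |
| SRS, plan graded major deviation | 4.4.6 | Out: the only dose is non-conforming |
| FSRT, plan graded major deviation throughout | 4.4.6 | Out: no conforming fraction |
| Dose or PTV modified at discretion before the first dose | 4.6 | Unclear: allowed by the protocol, but not said to count as protocol treatment |
| Major eligibility violation | 9.3 | Out of the statistical analysis; case report only |

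**Step 2. Whether the filter is the same in both arms**

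- Number of doses (section 4.4.5): SRS gives 1 and FSRT gives 12. A departure confined to part of the course removes nobody from FSRT. The same departure at the single SRS session removes the patient.
- Lower limits (sections 4.4.6 and 4.4.10): the floor for an acceptable variation is conformity 0.9 and coverage 0.8. In SRS it falls to 0.8 and 0.7 if brain constraints cannot otherwise be met. A conformity index of 0.85 can therefore be acceptable in SRS and is a major deviation in FSRT. A coverage of 0.75 behaves the same way.

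The first feature tends to drop SRS patients and the second FSRT patients. The rule is unequal, but its net balance cannot be read from the text.

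**Step 3. When membership can be known**

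Section 9.5 has safety looks after 50, 100 and 200 recruited patients. Systematic plan review comes after accrual (section 4.4.8). A set that depends on plan grade could not be applied at those looks as it would be at the end.

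**Step 4. Illustration of size**

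Inputs:
- p, the true necrosis rate among all irradiated patients in an arm: 5% to 20%, the range section 1.5 gives after SRS of larger metastases.
- n = 191 per arm (section 9.2), all taken as irradiated.
- f, the share excluded: 2%, 5% or 10%. Assumption.
- RR, the risk in excluded patients relative to the rest: 0.5, 1, 2 or 3. Assumption.

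If b is the rate in those kept, then p = (1 − f)·b + f·RR·b, so b = p / (1 − f + f·RR).

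Patients excluded: 191 × 0.02 = 3.8; 191 × 0.05 = 9.6; 191 × 0.10 = 19.1.

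| True rate p | f | RR 0.5 | RR 1 | RR 2 | RR 3 |
|---|---|---|---|---|---|
| 20% | 2% | 20.2% | 20.0% | 19.6% | 19.2% |
| 20% | 5% | 20.5% | 20.0% | 19.0% | 18.2% |
| 20% | 10% | 21.1% | 20.0% | 18.2% | 16.7% |
| 5% | 10% | 5.3% | 5.0% | 4.5% | 4.2% |

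Two cells worked out for p = 20%, f = 10%:
- RR = 3: 1 − 0.10 + 0.30 = 1.20, and 20% / 1.20 = 16.7%.
- RR = 0.5: 1 − 0.10 + 0.05 = 0.95, and 20% / 0.95 = 21.1%.

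For scale, the standard error of a 20% rate in 191 patients is √(0.20 × 0.80 / 191) = 2.9 percentage points.

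**The case against.** The strongest reply is that the phrase means only one dose of the protocol's radiotherapy. On this view section 9.3 contrasts patients who fully completed treatment with patients who received any of it, and the compliance words carry no weight. In support, section 9.3 does not cite section 4.4.6, section 4.4.6 ties plan grade to no analysis set, section 4.4.8 treats plan review as quality assurance, and the safety looks in section 9.5 carry no plan-quality restriction. This reading is plausible and may be what was intended. However, no sentence secures it, and the paragraph before uses the same phrase as a restriction. It also does nothing for the eligibility exclusion, which is a separate and explicit rule.

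It is also fair to say that no data are lost: section 8.1.3 requires all adverse events to be documented. That makes the repair cheap, but it does not decide who is analysed.

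Two stronger readings are tempting, and the document does not support them.

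- A reader might infer that modified regimens in general are dropped. They are not. One conforming fraction suffices, section 4.4.10 reductions are permitted, and section 4.6 is itself a protocol provision. Only changes made before the first dose are in doubt.
- A reader might infer that the excluded patients are those most likely to have toxicity, so that necrosis is understated. Section 4.4.10 does name the brain volumes receiving 10 and 12 Gy as predictors of necrosis, and a conformity index above 2.5 could raise them. But major deviations also include low conformity and low coverage, which mean under-treatment. A homogeneity index above 2.5 would need prescription below the 1/2.5 = 40% isodose, already outside the 50–80% and 80% of section 4.4.5, so it is an unlikely route to over-exposure.

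**Conclusion.** The point holds as a defect in the definition of the population. Read literally, section 9.3 leaves out of the toxicity analysis irradiated patients with an unacceptable plan, above all in the SRS arm where there is a single dose, and irradiated patients found ineligible. The status of patients modified under section 4.6 before their first dose is unclear. The rule can act unequally between arms, and its full application has to wait until after accrual.

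The direction and size of any resulting bias cannot be derived from the document. Bias is zero if excluded patients have the same risk as the rest, and it can run either way. Across the assumed ranges, a true rate of 20% would be reported as anything from 16.7% to 21.1%, a shift of −3.3 to +1.1 percentage points. At its largest this is about one standard error of a single arm's rate. These figures rest on assumed exclusion shares and risk ratios and are not estimates for this trial.

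The text should be corrected because the rule is wrong in principle and easy to repair, without any claim that it is known to hide toxicity.

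**What to change.** Replace the toxicity sentence in section 9.3 with a definition based on exposure, for example: *The toxicity set comprises every patient given one or more fractions of study radiotherapy, regardless of plan-quality grade, regimen modification or eligibility status, analysed by the treatment actually received.* Add that the exclusion for major eligibility violations does not apply to this set. Use the same definition for the safety looks in section 9.5.

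Optionally, add a table of toxicity by plan-quality grade, so that the effect of deviations is shown and not removed.

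The cost is a short text change carried into the analysis plan. Adverse events are already collected at every visit (section 5.3), so no new data, visits or patients are needed.

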9.4. Statistical analysis

Descriptive statistics will be used to check the balance of the treatment groups of the study population with regard to demographic and prognostic baseline data. Sensitivity analyses will be conducted if needed to adjust for relevant imbalances in the study population by appropriate modeling or stratification, including the corresponding co-variables. Adjusted and non-adjusted analyses will be compared and critically analyzed. With respect to the primary endpoint, the main analysis will account for the stratified randomization (stratified log-rank test).

Confirmatory analysis of the primary endpoint variable will be performed using a p-value of $p \leq 0.025$ (one-sided) as significance level.

All other parameters will be analyzed by descriptive statistics describing their frequencies, arithmetic means, standard deviations, median values, interquartile distances, ranges and, eventually, confidence intervals. If exploratory statistical analyses are performed for comparison of the different treatment arms or subgroups, p-values will be explicitly reported. As a rule, adjustment of significance levels for multiple analyses (multiplicity adjustment) will not be performed, so the p-values are considered to be descriptive and reflect a Type I error for the individual comparison and not for the overall experiment. Unless otherwise stated, two-sided tests will be used. The statistical methods listed below are usually suitable for the data and distributions expected in such studies. Their suitability will be assessed after data collection. If necessary, the choice of methods will be modified accordingly, and the respective results will be critically evaluated in a sensitivity analysis.

Toxicity and response rates as well as survival and progression-free survival rates at the specified time points will be calculated together with their exact confidence intervals and compared by either Fisher's Exact Test, the χ^2 Test or the Mantel-Haenszel test (Cochran-Armitage trend test), as appropriate for the type and extent of the variable.

The Wilcoxon-Mann-Whitney test will be used to test continuous data or scales in intergroup comparisons, and the Wilcoxon signed-rank test will be used to compare paired samples between different sampling times.

Time-to-event data such as time to local progression (TTLP), local progression-free survival (LPFS), and overall survival (OS) will be presented in life tables constructed using the KAPLAN-MEIER method (Kaplan et al. 1958) and compared using the log-rank test (Here, LPFS is defined like TTLP except that death not preceded by local progression will not be censored but counted as an event). If the assumption of "proportional hazards" underlying the Peto log rank test (Peto et al. 1972, Peto et al. 1976) clearly does not apply (Haybittle 1988), Gehan's generalized Wilcoxon test for comparing arbitrarily singly-censored samples will also be used as sensitivity analysis (Gehan 1965), preferably, as modified by Peto and co-workers and Prentice (Peto et al. 1972, Prentice 1978). Prospective stratification and other prognostic strata, if necessary, may be taken into account in further sensitivity analyses (Peto et al. 1976).

TTLP, the primary endpoint of the study, will be described and evaluated in another sensitivity analysis based on the cumulative incidence method (Gray 1988), in which death not associated with local progression will be treated as a competing risk event

Univariate consideration of prognostic factors will be performed by applying the above-mentioned methods accordingly. Multivariate analysis, if required, will be performed using the Cox proportional hazards regression model (Cox 1972).

Further details regarding the statistical analysis will be specified prospectively in a Statistical Analysis Plan before any analyses of treatment efficacy are carried out. As software, SPSS, R, TESTIMATE, and/or SQL will be used for analysis.

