1.6.2. Secondary objectives

- Improvement of the tolerability of local radiotherapy, as measured based on the endpoints CNS toxicity and, in particular, radiation necrosis in accordance with the Common Terminology Criteria for Adverse Events Version 5.0. Improved tolerability will also be measured as time to radiation necrosis.
- Improvement of the local control of irradiated brain metastases, as determined based on volumetric criteria. Volumetric criteria may have

important methodological advantages over traditional endpoints for the identification of treatment failure, especially in the case of large brain metastases. This study aims to improve our understanding of volumetric criteria and helps to further establish them.

Based on the *RANO-BM* criteria, progression is defined as an increase in volume of 72.8% or more (corresponds to a 20% increase in diameter for a perfect sphere). True local progression and radionecrosis are differentiated via a prespecified algorithm in the trial. If multiple metastases are treated in the trial, progression is defined as at least one metastasis fulfilling the criteria for progression.

- Assessment of quality of life (EORTC QLQ-C30 and QLQ-BN20)
- Improvement of local progression-free survival
- Improvement of overall survival
- Improvement of brain metastases-specific survival
- Time to distant brain failure

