2.4. Time schedule

Start of study:	Q3 2020
Start of recruitment:	Q1 2021
Duration of recruitment:	3 Jahre
Duration of follow-up:	2 Jahre
End of study:	2026

Follow-up is performed for progression/radionecrosis as well as for overall survival, toxicity and distant progression, respectively. In case of local progression, radionecrosis or distant progression, follow-up for the other events as well as toxicities and overall-survival continues. In case of radionecrosis, follow-up for progression continues, if not determined by histology, as progression can occur after a lesion has experienced radionecrosis. Conversely, in case of progression, follow-up for radionecrosis for the respective lesion ends.

3. Selection of study population

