9.2. Sample size calculation

On the basis of available retrospective and dose-response relationship data, it is expected that SRS will result in a 12-month local tumor control rate of approximately 65% and that FSRT can increase this rate to about 80% (cf. Section 1.4). This difference is considered to be clinically significant. A sample size of N=191 evaluable cases each in the experimental and control arm, respectively, corresponding to a total of 382 patients, is required to detect a significant difference i.e. an increase in TTLP at least this large at 12-month follow-up in a randomized comparison. The number of TTLP events to be observed is 82. This calculation is based on the following framework conditions:

- The risk of making a false claim of superiority of FSRT which actually does not exist is 2.5% (α error, one-sided).
- The success rate for identifying superiority of FSRT over the control arm which actually exists is 80% (power, $1-\beta$ error).
- Assuming an exponential decline of TTLP curves
- As this is a basically palliative setting with disseminated disease, it must be considered that about half of the patients will be dead at 12-month follow-up. Consequently, a considerable proportion of patients

will have a truncated follow-up in which no event related to the primary endpoint occurs. The extent of this quasi-drop-out process is estimated to be $\leq 50\%$ and is also assumed to be exponentially distributed over the 12 months.

- Duration of follow-up for all patients: at least 12 months or until the incidence of local progression.

Note: Due to patient entry kinetics during the planned recruitment, and due to the intended follow-up period of up to 24 months for each patient (cf. section 5.1.4), the follow-up periods for a considerably number of patients, mainly those randomized early, may be significantly longer than 12 months by the end of the study. This should result in an increase in the expected number of observed events, leading to a further increase in power of the study. Since this effect is difficult to quantify (especially due to death as a competing risk event), it is not taken into account in sample size calculation, to be on the safe side. Therefore, the recruitment period is not included among the parameters provided above.

Sample size estimates were calculated based on the method of LACHIN and FOULKES (Lachin et al. 1986), applying the software NSURV (idv, Gauting, Germany).

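### Section 9.4 fixes uncensored-proportion methods for survival and progression-free survival rates that it also analyses by Kaplan-Meier, and names a competing-risk method for TTLP but not for radionecrosis

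*Protocol*

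**What the plan says.** Protocol section 9.4 puts toxicity, response, survival and progression-free survival rates in one sentence: "survival and progression-free survival rates at the specified time points will be calculated together with their exact confidence intervals". The rates are then to be "compared by either Fisher's Exact Test, the χ^2 Test or the Mantel-Haenszel test (Cochran-Armitage trend test"), whichever suits the variable.

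The next part of section 9.4 covers "Time-to-event data such as time to local progression (TTLP), local progression-free survival (LPFS), and overall survival (OS"), which are to be shown by Kaplan-Meier and compared by log-rank. LPFS follows the TTLP definition, except that "death not preceded by local progression will not be censored but counted as an event".

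Section 9.1 censors TTLP at loss to follow-up and at unauthorised treatment of the target lesions, and LPFS inherits both. Sections 6.11 and 6.12 add withdrawal by the patient or by the physician.

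On radionecrosis, section 1.6.2 says: "Improved tolerability will also be measured as time to radiation necrosis". No analysis method is named for it. A competing-risk method appears once: "TTLP, the primary endpoint of the study, will be described and evaluated in another sensitivity analysis based on the cumulative incidence method". Section 9.2 expects that "about half of the patients will be dead at 12-month follow-up". Section 2.4 adds: "Conversely, in case of progression, follow-up for radionecrosis for the respective lesion ends".

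**The concern.** Exact binomial limits and Fisher or chi-square tests treat each patient as a known success or failure at the time point. A patient censored earlier has to be counted as event-free or left out, and each choice biases the rate. Because section 9.4 also assigns Kaplan-Meier to OS and LPFS, a report could carry two different 12-month figures for one endpoint. The section leaves the suitability of methods to be judged after data collection, so nothing says in advance which figure counts.

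For radionecrosis the issue is different. If time to radionecrosis is handled as the other time-to-event data are, death is censored. One minus Kaplan-Meier then estimates the risk in a hypothetical population in which nobody dies, not the share of patients who develop radionecrosis. The protocol sees this for TTLP and adds cumulative incidence there, but not for the main tolerability endpoint. The absolute risk of radionecrosis in each arm would be overstated in the benefit-risk account.

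**Working it through.** **Inputs.** From section 9.2: 12-month local control of 65% (SRS) and 80% (FSRT), exponential curves, and a 50% loss process by 12 months that is attributed to death. From section 1.5: radionecrosis frequency of 5 to 20% after SRS. Hazards per year:
- death d = ln 2 = 0.693
- progression p = -ln 0.65 = 0.431 (SRS) and -ln 0.80 = 0.223 (FSRT)

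**The plan's own figure.** With m = ln 2 as loss hazard, P(λ) = λ/(λ+m) × (1 - exp(-(λ+m))) gives 0.2587 (SRS) and 0.1461 (FSRT). The Lachin-Foulkes formula is n = [(1.960 √(2v(λ̄)) + 0.842 √(v(λ1)+v(λ2))) / (λ1-λ2)]², with v(λ) = λ²/P(λ) and λ̄ the mean of the two hazards. It gives 190.7, hence 191 per arm, as stated. The hazards used here are therefore the protocol's own.

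**Step 1. Fixed-time OS as a simple proportion.** True 12-month OS is 50%. The loss fraction c is an assumption, because the protocol gives no figure for loss other than death. With loss hazard l = -ln(1-c) and T = l + d:
- observed deaths by 12 months = d/T × (1 - exp(-T))
- known alive at 12 months = exp(-T)

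| Assumed loss | Observed dead | Known alive | OS if lost count as alive | OS if lost are dropped |
|---|---|---|---|---|
| 0% | 50.0% | 50.0% | 50.0% | 50.0% |
| 5% | 48.9% | 47.5% | 51.1% | 49.3% |
| 10% | 47.7% | 45.0% | 52.3% | 48.5% |
| 20% | 45.4% | 40.0% | 54.6% | 46.8% |

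Without loss the proportion is exactly right, despite 50% mortality. Under independent censoring, Kaplan-Meier estimates 50% in every row.

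**Step 2. Radionecrosis with death competing.** Let r be an assumed net 12-month risk, g = -ln(1-r), and t the time in years.
- One minus Kaplan-Meier, death censored: 1 - exp(-gt)
- Actual incidence: g/(g+d) × (1 - exp(-(g+d)t))

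For r = 15%, g = 0.1625 and g + d = 0.8557:
- 12 months: 15.0% against 0.1625/0.8557 × (1 - exp(-0.8557)) = 10.9%
- 24 months: 27.8% against 0.1625/0.8557 × (1 - exp(-1.7113)) = 15.6%

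| Net 12-month risk | 12 months: 1-KM / incidence | 24 months: 1-KM / incidence |
|---|---|---|
| 5% | 5.0% / 3.6% | 9.8% / 5.3% |
| 10% | 10.0% / 7.3% | 19.0% / 10.5% |
| 15% | 15.0% / 10.9% | 27.8% / 15.6% |
| 20% | 20.0% / 14.6% | 36.0% / 20.5% |

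The overstatement is about 1.4-fold at 12 months and 1.8-fold at 24 months.

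**Step 3. Stop of radionecrosis follow-up at progression.** Assume one lesion per patient and the same radionecrosis hazard in both arms. The observed proportion is then g/(g+d+p) × (1 - exp(-(g+d+p)t)). For r = 15% at 24 months:
- SRS: 0.1625/1.2865 × (1 - exp(-2.573)) = 11.7%
- FSRT: 0.1625/1.0788 × (1 - exp(-2.1576)) = 13.3%

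The spurious difference is about 1.6 points against FSRT. Across r of 5 to 20% it is 0.3 to about 1 point at 12 months and 0.6 to about 2 points at 24 months.

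**The case against.** Three stronger readings are tempting, and the protocol supports none of them.

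- **High mortality makes simple proportions invalid for OS and progression-free survival.** It does not. Death is the event in both, and the 0% row of Step 1 shows no bias. Follow-up is planned to two years and survival follow-up continues after progression, so 12-month status may be known for most patients. What stands is that loss, withdrawal and, for LPFS, non-protocol treatment do censor, and that two methods are fixed for the same endpoints.
- **The protocol prescribes Kaplan-Meier for radionecrosis.** It names only TTLP, LPFS and OS, as examples. Radionecrosis, distant brain failure and brain-metastasis-specific survival come under Kaplan-Meier by inference, and section 9.4 defers further detail to the SAP. What stands is that this is the only time-to-event method that could cover them, and that the competing-risk analysis is expressly tied to TTLP.
- **Ending radionecrosis follow-up at progression seriously distorts the arm comparison, so progression should be a competing event.** The rule applies to the progressed lesion only, and section 7.2 lets one patient have both events. The one-lesion figures in Step 3 are therefore an upper illustration. The 1.6 points compare with a standard error of √((0.117×0.883 + 0.133×0.867)/191) = 3.4 points, and they count against FSRT, so they do not flatter it. Cumulative incidence with progression competing would return the same 11.7% and 13.3%, so it would not remove the effect.

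It is also fair that a crude toxicity proportion does estimate incidence in the presence of death if follow-up is complete, that log-rank on cause-specific hazards remains a usable comparison, and that all these analyses are secondary with descriptive p-values.

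**Conclusion.** The point holds in limited form. Section 9.4 states a rule that misestimates fixed-time OS and LPFS rates whenever status is unknown, and it contradicts the Kaplan-Meier rule for the same endpoints. At an assumed 10 to 20% loss the error in 12-month OS is about 2 to 5 points upward or 1.5 to 3 points downward, depending on how lost patients are handled. For radionecrosis, extending the Kaplan-Meier wording to it would overstate absolute risk about 1.4-fold at 12 months and 1.8-fold at 24.

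These sizes rest on constant, independent hazards, the protocol's 50% mortality at 12 months, and assumed loss and radionecrosis risks. The primary stratified log-rank test, its competing-risk sensitivity analysis and the sample size are unaffected. The matter deserves correction but does not threaten the trial's main conclusion.

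**What to change.** Amend section 9.4 and carry the wording into the SAP:

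- Take OS and LPFS rates at fixed times, their confidence limits and their comparison between arms from the Kaplan-Meier estimates.
- Keep exact limits and Fisher or chi-square tests for outcomes observed in everyone, such as acute toxicity.
- Report radionecrosis, distant brain failure and brain-metastasis-specific death by cumulative incidence (Gray), with death as the competing event; for the last, death from other causes. Give cause-specific hazard ratios alongside.
- Do not make local progression a patient-level competing event for radionecrosis by default. Use the cause-specific comparison for the arm contrast, state how progressed lesions are handled, and note that unequal progression shifts crude proportions slightly against FSRT.

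The cost is a change of wording and a few more tables. Gray's method is already planned for TTLP, and no extra data are needed.
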